## LIST OF ABBREVIATIONS

ADE	Adverse Drug Event
AE	Adverse Event
ADR	Adverse Drug Reaction
AHSN	Academic Health Science Networks
ARC KSS	Applied Research Collaboration Kent, Surrey & Sussex
BGS	British Geriatrics Society
CI	Chief Investigator
DMS	Discharge Medicines Service
GCP	Good Clinical Practice
GP	General Practitioner
НШВН	Healthwatch Brighton and Hove
ММР	Medicines Management Plan
MRH	Medication-Related Harm
NHS	National Health Service
PCIE	Public and Community Involvement and Engagement Committee
PI	Principal Investigator
PIS	Participant Information Sheet
R&D	Research & Development
RCT	Randomised Control Trial
REC	Research Ethics Committee
RPM	Risk Prediction Model
RPT	Risk Prediction Tool

SOP	Standard Operating Procedure
U3A	University of the Third Age
UPIN	Unique Participant Identification Number
WHO	World Health Organisation

## **STUDY SUMMARY**

Study Title	Implementation of a medicine management plan (MMP) to reduce medication-related harm (MRH) in older people post-hospital discharge: a randomised controlled trial
Internal ref. no. (or short title)	Reducing medication-related harm (MRH) in older people
Study Design	Randomised Controlled Trial
Study Participants	Older people >65 years who are due to be discharged from hospital
Planned Size of Sample (if applicable)	682 participants
Follow up duration (if applicable)	8 weeks
Planned Study Period	18 months
Research Question/Aim(s)	To assess the clinical and cost effectiveness of a risk prediction tool (RPT)-informed Medicine Management Plan (MMP) linked to the NHS Discharge Medicine Service (DMS) compared to the NHS DMS alone in reducing MRH in the 8 weeks post-hospital discharge.

#### FUNDING

FUNDER	FINANCIAL AND NON-FINANCIAL SUPPORT GIVEN
Applied Research Collaboration Kent, Surrey, and Sussex (ARC KSS)	£74,479

## ROLE OF STUDY SPONSOR AND FUNDER

The study sponsor is the University of Sussex represented by [name]. The University of Sussex is overseeing the conduct of this research study in compliance with MHRA and GCP regulations. The University of Sussex will assume overall responsibility for the initiation and management of the study. The study is funded by ARC KSS.

The study funder has not and will not have input into the study design, conduct, data analysis and interpretation, manuscript writing, or dissemination of results. The chief investigator and study research team have developed the study design, and will be responsible for the study conduct, data collection, data analysis and interpretation, manuscript writing, and dissemination (writing study report, and submission to scientific conferences, and scientific journals). The sponsorship committee at Sussex University has provided input into the study documents, and that input has been included into the final study documents.

## **STUDY FLOW CHART**

See appendix for a schematic overview of the participant's journey through the study. See appendix for a timeline providing an overview of the study management.

## 1 BACKGROUND

Medication Without Harm is the World Health Organisation's (WHO) Third Global Patient Safety Challenge. It aims to "reduce the level of severe, avoidable harm related to medication by 50% over 5 years, globally" (1). Medication-related harm (MRH) includes harm from adverse drug reactions (ADR), non-adherence and medication errors (2).

In a large, prospective UK study of 18,820 patients, the prevalence of an ADR-related admission was 6.5% with the average age of 76 years old and an estimated cost of £466 million annually (3). A large, retrospective study of adverse events (AE) across 58 US hospitals identified 5077 cases of inpatient admissions in the over 65s from 99,628 emergency department visits with half occurring in those older than 80 (4). A meta-analysis shows elderly patients are 4 times more likely to be admitted with an ADR compared to younger patients (5). In a systematic review of MRH in older adults, between 17-51% patients' experience MRH within 30 days post-discharge (2). Our study team have shown that in the 8 weeks following hospital discharge, 37% of over 65s experienced MRH with an estimated cost of £400million annually (6).

Factors contributing to MRH in older people include multimorbidity and polypharmacy (7), age-related changes in pharmacokinetics and pharmacodynamics (8) and medication non-adherence (9). Transition of care at hospital discharge is high-risk for occurrence of MRH with multiple contributory factors: the impact of acute illness, an inpatient stay and patient deconditioning (10), medication discrepancies at admission or discharge (11), patient/carer education on the discharge medication regimen and use of new medications (12), and poor communication between secondary and primary care (13,14).

The WHO identifies three key target areas to protect patients from MRH: high-risk situations, polypharmacy and transitions of care (1). The WHO defines high-risk situations as certain clinical circumstances in which the impact of MRH may be greater; this includes elderly individuals and those with hepatic or renal impairment. Discharge of an elderly individual is an especially high-risk situation encompassing many factors that may lead to MRH.

The NHS Discharge Medicines Service (DMS) is a newly-commissioned community pharmacy service aimed to reduce avoidable post-discharge MRH based on an initiative led and delivered by the Academic Health Science Networks (AHSNs). The DMS is a system of communication allowing hospital pharmacists to refer patients to community pharmacists to ensure they receive adequate support post-discharge. The evidence has been informed by multiple studies showing reduced readmission rates and shorter hospital stays (15–18).

Although effective, patient selection in the NHS DMS is based on hospital pharmacist judgement and not on any evidence-based risk stratification data (19). NHS England support risk stratification using risk prediction models (RPMs) in identifying individuals who will derive the most benefit from target interventions (20). Risk stratification is increasingly important in a healthcare system challenged by an ageing population (21) with an increasing prevalence of healthcare use due to MRH (22).

Six prior RPMs exists; McElnay (23), the BADRI Model (24), the GerontoNet ADR risk score (25), Trivalle (26), the PADR-EC score (27), and the ADRROP prediction scale (28). These RPMs do not predict the risk of MRH occurring in the post-discharge period. No impact studies of these tools have been published. They predict the risk of inpatient ADR/ADE (24–26,28) or risk of an unplanned admission being due to ADR/ADE (23,27).

The PRIME model has been developed and internally validated as the first RPM to predict the absolute risk of an older person experiencing MRH in the 8-week post-discharge period (29). It was developed though a large multicentre, prospective observational cohort study. The PRIME model consists of eight variables routinely collected in hospital (age, gender, antiplatelet drug, sodium level, antidiabetic drug, past ADR history, number of medicines, and living alone). This tool considers demographic, medical and social factors in predicting the absolute risk of MRH. The PRIME tool calculates risk of definite MRH; MRH that was classified as 'probable' or 'possible' was excluded.

Currently, there are no tools in clinical practice to target interventions to high-risk patients in the community following hospital discharge. The PRIME model is the first RPM able to predict risk of MRH in older adults in the community in the 8 weeks post-discharge.

## 2 RATIONALE

Medication-related harm (MRH) for this study will include adverse drug reactions, medication errors, and a failure to take/receive medication, either following non-adherence or a failure in the supply chain.

The WHO identifies transition of care as a key area in which it is necessary to protect patients from harm (1). Previous interventions in the post-discharge period have been ineffective (30–33). The evidence-based NHS DMS has been shown to decrease readmission rate and shorten length of hospital stay (15–18). Patient selection is based on hospital pharmacist judgement and not on any evidence-based risk stratification data (19). Clinical judgement alone is not sufficient in predicting MRH in older patients (34).

NHS England recognises risk stratification using RPMs can target those at greatest risk and those who are most likely to derive benefit from intervention (20). The PRIME tool is the first tool to predict absolute risk of MRH in the 8 weeks post-discharge period and is a better predictor than clinical judgement (34). The medicine management plan was developed through a study funded by the British Geriatrics Society (BGS) led by [name] and [name] in consultation with patients, carers and healthcare professionals.

The PRIME team in collaboration with AHSN-KSS will implement a risk-stratification approach linked with the NHS DMS. The study will recruit patients aged 65 and older discharged from 4 acute hospital trusts. The control arm will consist of NHS DMS care only. The intervention arm will consist of NHS DMS with a specific medicines management plan (MMP). The MMP will be as follows:

- 1. A copy of the discharge summary
- 2. Specific education about possible medication-related harm from the discharge medications. Education will be delivered by the ward pharmacist and / or the ward doctor at the point of discharge.
- 3. Clear guidance on who to contact (their GP or their community pharmacist) if they experience any MRH.

- 4. The name and contact of the community pharmacist will be provided by the ward pharmacist.
- 5. A copy of the percentage/ probability of harm from medication calculated using the PRIME study RPT, and presented as a visual analogue scale will be offered to patients and (if available) their carers. See Appendix for document.

## **3** THEORETICAL FRAMEWORK

Current risk stratification in clinical practice for MRH in older adults is based on clinical judgement. Clinical judgement is not useful in predicting MRH (34). Currently, MRH risk prediction tools are not routinely used in clinical practice, as existing tools have not been assessed for impact and implementation (35). The PRIME tool has been transparently developed and validated. The MMP has been developed with consultation from patients and carers. To satisfy the next stage of risk-prediction model creation, the impact of the tool will be assessed on a new sample of individuals. Targeted interventions at high-risk individuals may be a clinically and cost-effective solution in reducing rates of MRH in older adults.

## 4 RESEARCH QUESTION/ AIM

## 4.1 Primary Research Question

Will a Medicines Management Plan linked to the NHS DMS be more effective than the NHS DMS alone in reducing rates of MRH?

## 4.2 Objectives

- I. To measure and compare the rates of MRH in the two groups.
- II. To measure the costs of delivering the intervention and any associated MRH-related service use in the two groups across the 8-week study period. To perform modelling to provide national cost estimates.
- III. To undertake a process evaluation.

## 4.3 Outcome

A clinical, economic and service evaluation of NHS DMS alone compared to a MMP linked with the NHS DMS in reducing MRH

## 5 STUDY DESIGN AND METHODS OF DATA COLLECTION AND DATA ANALYSIS

Participants will be recruited across 4 sites: Royal Sussex County Hospital in Brighton, Ashford and St Peter's Hospital in Ashford, Medway Hospital in Kent, and Royal Devon Hospital in Exeter. The proposed study is a Randomised Control Trial (RCT), as patients will be randomised into either the NHS DMS alone (control arm/standard care), or RPT-stratification plus MMP linked to the NHS DMS (intervention arm).

## Sample size/power details

In determining the sample size, let the proportion of subjects developing MRH when given the standard care be  $p_1$ , while the proportion of subjects developing MRH among those put through intervention arm be  $p_2$ . Common measures for comparing whether the two proportions are statistically significantly different are:

- 1. Difference,  $\delta = p_1 p_2$
- 2. Odds-ratio,  $\Psi = \frac{p_1/(1-p_1)}{p_2/(1-p_2)}$

Then the two equivalent hypotheses for evaluating whether the two proportions are different are H0: $\delta$ =0 and H0: $\Psi$ =1. The values of  $\Psi$  close to 1, indicate no difference and those further from 1 are the ones that specify differences that may be clinically important. The sample size formula can be expressed so that the only parameters needed are the prevalence of MRH in the population receiving standard care and odds-ratios and there is no need to directly incorporate  $\delta$  in calculations. In this case  $\Psi$  is the fixed parameter and sample size can be calculated for various values of prevalence. The advantage of using the odds-ratios as fixed is that it is straightforward to define clinically important differences from a range of admissible values. Once desired value of odds-ration is selected, the corresponding values of  $\delta$  (defining clinically important difference), can be computed for the observed prevalence value.

The choice of the value of odds-ratio to use is based on the range of values of odds-ratios that normally show up as significant in statistical analyses. As it is not expected that the two arms of the study would be dramatically different, we recommend the choice of medium values of odds-ratios.

A systematic review of MRH in older adults found that between 17% and 51% of patients experience MRH within 30 days of hospital discharge. In the UK, approximately 28% of older adults ( $\geq$ 65 years) use health services due to MRH within the 8 weeks following hospital discharge (6). Therefore, our choice of the prevalence to use in the sample size calculation is limited to MRH rates between 20% - 40%. In particular, we take the prevalence of MRH among the group under standard treatment to be 35% and an odds-ratio of 1.6 is considered large enough to result in a clinically important difference in MRH rates between arm 1 and arm 2. These choices of  $p_1$  and odds-ratio corresponds to  $\delta$ =0.098.

To determine the required sample size to estimate a difference  $\delta$  that is clinically relevant, the method of Fleiss, Tytun, and Ury (53) was used. This method has been implemented in the function "bsamsize" given in R package "Hmisc" (54). To calculate sample size using this method, one needs to provide the following parameters: the prevalence of MRH among people given standard treatment ( $p_1$ ) and among people given the new care/intervention ( $p_2$ ), odds-ratio ( $\Psi$ ), the statistical power we wish to achieve, and the margin of error.

We found that a sample size of n=682 (341 subjects on each arm) will be required to detect  $\delta$ =0.098 (i.e., odds-ratio=1.6), with 80% statistical power, and a 5% margin of error, if we assume that the prevalence of MRH among those on standard treatment is 35%.

## **5.1 CLINICAL EFFECTIVENESS**

## **Baseline Data Collection**

The baseline data collected and methodology will correspond to that of the original PRIME Study (36). Consenting participants (and participants consenting through their consultee) will have baseline data collected by a trained research nurse.

Demographic (age, gender, ethnicity), clinical (discharge diagnosis, co-morbidities, renal function, electrolytes, hepatic function), and social indicator data (living arrangements and care package on discharge) will be collected. Admission and discharge medication data (drug name, frequency, dosage) and use of compliance aids will be collected and coded using the WHO-ATC code (37). The above are routine clinical data, and so can be collected directly from the hospital notes.

Validated tools will be used to collect data on comorbidities, nutritional status, physical function and cognitive function. The Charlson Comorbidity Index (CCI) which predicts 10-year survival in patients based on age and comorbid status will be collected by the research nurse (38). The Malnutrition Universal Screening Tool (MUST) score is a nutritional screening tool routinely used on elderly care wards to stratify and manage overall risk of malnutrition (39). The Barthel ADL Index is a validated scale used to measure performance in activities in daily living (ADL) (40). Barthel's Index, MUST and Abbreviated Mental Test Score (AMTS) will be collected from patients' notes only.

Data collection will take place using a form designed to be scanned into an electronic database. At the point of data collection, each participant will be allocated a unique participant identification number (UPIN). Data will be anonymised prior to upload to the electronic database. The anonymised data base will be stored on NHS and University Computers. Hard copy non-anonymised data will be stored in locked cabinets in each respective study site with access provided to the CI and each respective PI only. Hard copy data will be destroyed in compliance with local protocol at 3 years.

## Follow up Data Collection

The research pharmacist will conduct a telephone interview and GP records review after eight weeks postdischarge for every participant. The phone interview with study participants will take form 5 minutes to 30 minutes depending on the amount of information study participants have to share with the pharmacist around your medications. A standardised questionnaire will determine whether the patient has experienced MRH. Suspected ADRs, medication adherence, and primary/secondary care usage will be explored. MRH severity will be assessed using the Morimoto scale (45). If an ADR is suspected, causality will be assessed using the Naranjo algorithm (46). Medication adherence will be assessed using the Morisky scale (47).

Participants re-admitted within the study time frame will be reviewed prospectively to ascertain MRH as the primary end-point. They will not re-enter the study as new participants.

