## Table 1: Possible risks and management strategies

Possible risk	Plan to manage risk	Study member/ team managing risk
Delay in securing ethics approval	Early ethics approval submission as soon as the funding decision is known	Chief Investigator (CI) [name].
Not recruiting to time and target	Opening additional study sites: Princess Royal Hospital, Haywards Heath, and St Thomas', SouthamptonHospital with funding from Impact Acceleration Award (IAA). Royal Devon Hospital in Exeter is a study site and this makes the study eligible for adoption into the national portfolio of ageing research studies.	CI and study advisory committee, and the PCIE committee
Study nurses and trial pharmacists' familiarity with the study recruitment procedures	Training and supervision delivered on a regular basis. Two pharmacists providing cross cover for data collection in each study site.	[name], CI and Trial coordinator.
Loss to follow up in study participants	Regular updating of CRF for study participants	DMS team, Trial coordinator, and study advisory committee
Coordination between clinical teams and research team	The service evaluation work package	[name] and CI.

Generalisability of study results	National scaling up of the study findings	National Adoption committee,
		and service evaluation package

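### The protocol describes no masking of whoever ascertains or verifies MRH, while only the MMP arm is taught about MRH and told whom to contact

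*Protocol*

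**What the plan says.** **Ascertainment.** Section 5.1, Follow up Data Collection: "The research pharmacist will conduct a telephone interview and GP records review after eight weeks postdischarge for every participant". A standardised questionnaire decides whether MRH occurred. Naranjo is applied if an adverse drug reaction is suspected, Morimoto grades severity, and Morisky measures adherence. Readmitted participants are also reviewed for MRH, which that section names as the primary endpoint. The Study Management Timeline gives study pharmacists continuing support in verifying MRH in unclear cases.

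**Intervention.** Section 2 gives the control arm the NHS Discharge Medicines Service (DMS) alone, and the intervention arm the same service plus the Medicines Management Plan (MMP). The plan includes "Specific education about possible medication-related harm from the discharge medications" and "Clear guidance on who to contact (their GP or their community pharmacist) if they experience any MRH". It also offers the patient a copy of the calculated risk of harm. The education comes from the ward pharmacist and/or ward doctor.

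**Staffing.** Section 5.2 refers to research nurses and pharmacists who create the plans. Table 1 provides "Two pharmacists providing cross cover for data collection in each study site".

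**Masking.** The protocol does not mention masking of the interviewer, the records reviewer or the verifier. Nor does it say that any of them knows the allocation.

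**The concern.** MRH is a judgement. Someone must decide whether a symptom, a missed medicine or an admission is medication-related, and the protocol itself expects some cases to be unclear. Two mechanisms could make recording differ by arm.

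- **Participant side.** Education about harm can make intervention-arm participants more likely to recognise and report it at interview. Advice to contact the GP can also generate entries in the GP record. The record review is therefore not fully independent of the intervention. This mechanism raises recorded MRH in the intervention arm and hides benefit.
- **Assessor side.** Participants know what they received and may say so in a conversation about their medicines lasting 5 to 30 minutes. An assessor who learns the arm and expects benefit may classify fewer events as MRH in the intervention arm, which creates apparent benefit.

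The two act in opposite directions, and the data as collected would not separate them. A larger sample would not help. This is also not something a statistical analysis plan can repair: who assesses the endpoint, and what they know, is settled by the time the interviews are done.

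**Working it through.** **Inputs** (Sample size/power details)
- Control rate: "we take the prevalence of MRH among the group under standard treatment to be 35" per cent, so p1 = 0.35.
- Effect: "an odds-ratio of 1.6 is considered large enough to result in a clinically important difference in MRH rates", so OR = 1.6.
- Error rates: "with 80% statistical power, and a 5% margin of error". The margin of error is read as alpha. Sidedness is not stated; two-sided 5% reproduces the sample size.
- n = 341 per arm, 1:1.

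**Step 1: reproduce the plan's figure.**
- Intervention odds = (0.35/0.65)/1.6 = 0.3365, so p2 = 0.3365/1.3365 = 0.2518 and the difference is 0.0982.
- With mean proportion p̄ = 0.3009, n = [1.960·√(2p̄(1−p̄)) + 0.842·√(p1(1−p1)+p2(1−p2))]² / 0.0982² = 341.2 per arm. That is 682 in total, or 684 if rounded up.
- Power at 341 per arm is 80.0%. The sample size is not in error on this point.

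**Step 2: planned true effect, greater detection in the intervention arm.** Hold the recorded control rate at 0.35 and let the recorded intervention rate be q2 = 0.2518·r, where r is detection relative to control (assumed). Power = Φ[(d − 1.960·SE0)/SE1], where d = 0.35 − q2, SE0 is the pooled standard error and SE1 the unpooled one, plus a negligible opposite tail.

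| r | q2 | d | OR | Power |
|---|---|---|---|---|
| 1.00 | 0.252 | 0.098 | 1.60 | 80% |
| 1.05 | 0.264 | 0.086 | 1.50 | 68% |
| 1.10 | 0.277 | 0.073 | 1.41 | 54% |
| 1.20 | 0.302 | 0.048 | 1.24 | 27% |

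At r = 0.35/0.2518 = 1.39 the recorded difference disappears.

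**Step 3: no true effect, under-recording in the intervention arm.** The control rate is 0.35 and the recorded intervention rate is 0.35·(1−u), with u assumed. The last column is the two-sided rejection probability from the same formula.

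| u | Recorded rate | Rejection |
|---|---|---|
| 0 | 0.350 | 5% |
| 5% | 0.3325 | 8% |
| 10% | 0.315 | 16% |
| 14% (5 points: 0.05/0.35) | 0.300 | 29% |

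Over-recording of 5% and 10% with no true effect gives nearly the same rejection rates (7.6% and 15.7%), but in the direction of apparent harm.

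**The case against.** **The assessor may in fact be masked.** The protocol is silent, and a reader might infer an unmasked assessor. The documents do not establish that. What stands is narrower: no step keeps the allocation from the assessor, and participants can reveal it.

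**Delivery and assessment are different named roles.** The ward pharmacist or doctor educates; the research pharmacist follows up. A reader might infer from section 5.2 and Table 1 that the same people do both, but neither place says so. What stands is that no rule keeps the roles apart.

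**The endpoint is not patient report alone.** Every participant in both arms gets the same questionnaire and GP-record review, and readmissions are reviewed as a further source. Asking everyone actively makes the endpoint less dependent on spontaneous reporting. This protection is real but partial, because one arm is told to contact the GP and attributing an admission to medicines is still a judgement.

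**Larger losses of power can be computed, but they mix two things.** If 35% is taken as true harm, with detection of 80% in controls and 95% in the intervention arm, the recorded rates are 28.0% and 23.9% and power is 23%. But equal 80% detection in both arms already lowers power to 67%. The protocol's background rates come from recorded harm, so imperfect detection is plausibly already inside the 35%. With the recorded control rate held at 35%, the same 95/80 ratio gives 30%. The tables above isolate the differential part.

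**The two biases may partly cancel.** This is correct. It is why the net direction is left open, and why the documents do not support saying that no result could be read as an effect on harm.

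**Conclusion.** The point holds as an uncontrolled risk to the sole primary endpoint, not as a demonstrated bias. Followed as written, the protocol leaves detection of MRH free to differ by arm. A positive or null result could then not be attributed with confidence to harm alone.

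The planned difference is 9.8 points, so modest differences matter. A 10% relative gain in detection takes power from 80% to 54%, and 10% under-recording with no true effect raises the rejection rate from 5% to 16%. At 5% the consequences are smaller: 68% power and 8% rejection. These figures rest on assumed detection ratios and on reading the 35% as a recorded rate. The actual size and net direction cannot be determined from the protocol.

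**What to change.** Amend section 5.1 as follows.

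- **(a) Assessor.** The 8-week interview, GP-record review and readmission review are done by a study pharmacist at the site who had no part in that participant's plan or discharge, drawing on the two already in place. The follow-up form carries no arm field, a script asks participants not to mention the plan, and any unmasking is logged.
- **(b) Verification.** Unclear cases are verified on a summary with the arm redacted.
- **(c) Supportive analysis.** MRH identified through A&E attendance or readmission, already collected under section 5.2, is pre-specified as a supportive analysis of the primary endpoint and judged on arm-redacted records.

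**Cost.** Protocol wording, a form, a script and a rota rule, with no extra visits and no planned extra staff. Keep assessment within the site. Telephoning from another site would conflict with the limits on identifiable data in section 5.1 (Baseline Data Collection) and section 8.6, and would need changes to data access.

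**Downside.** Some unmasking will still occur. Masking the assessor does not remove differences in what participants report; (c) checks these only in part and has fewer events.
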